The FIRST-ABC (First-line support for Assistance in Breathing in Children feasibility study) trial is a randomised open label feasibility trial comparing high flow nasal cannula (HFNC) with continuous positive airway pressure (CPAP) to demonstrate feasibility for a full randomised controlled trial (RCT) for non-invasive respiratory support in critically ill children. The study design included the recruitment of 120 sick children from three NHS hospitals over six months where consent will be sought from the parents/guardians of the children, usually before CPAP or HFNC is started, unless emergency life-saving treatment is required, in which case consent will be deferred until there is more time to discuss the study with the parents/guardians of the children. The flow chart of the study is illustrated in Figure 1 below.

The purpose of this Statistical Analysis Plan (SAP) is to outline the planned analyses to be carried out to support the completion of the Final Report to the study funder and for inclusion in manuscripts for publication in the scientific literature. Additional exploratory analyses, which may not have been identified in this SAP, may also be performed. Any unplanned analyses not identified in this SAP will be clearly outlined as such in the respective Report/manuscript.

This SAP would be agreed in advance of inspecting the outcome data for the Trial, so that data-derived decisions in the analyses are avoided.

Figure 1: Study flow chart

2. Study objectives

2.1 Primary objectives

The primary objective of this study is to determine the feasibility of an RCT of HFNC versus CPAP in critically ill children. This objective was measured based on the following endpoints:

- i. Assess the number of eligible patients in Group A (step-up) and Group B (step-down)
- ii. Assess the acceptability of using a mixed model of consent (prospective and deferred)
- iii. Assess the feasibility of randomising at least 50% of eligible patients
- iv. Test the practical aspects of implementing the study protocol in terms of initiation, maintenance and weaning of the study intervention
- v. Assess whether a modified COMFORT score (COMFORT score minus the respiratory component) can be used to measure patient tolerance to CPAP/HFNC
- vi. Assess the feasibility of using the Parental Stressor Scale: PICU (PSS:PPICU) to measure parental stress 24 hours after the initiation of CPAP/HFNC

2.2 Secondary objectives

The secondary objectives are:

- i. To determine the rate of intubation within 72 hours of randomisation
- ii. To determine the rate of treatment failure (i.e. require either crossover or escalation to other forms of ventilation within 72 hours of randomisation)
- iii. To assess safety of the study treatments during the period the children were receiving non-invasive respiratory support
- iv. To assess physiological effects in the first 24 hours after the initiation of CPAP/HFNC
- v. To assess effects on patient outcome (i.e. Length of PICU and hospital stay, length of invasive ventilation, length of non-invasive

support, ventilator-free days at day 28, PICU mortality, hospital mortality)

3. Methods

3.1 Trial design

A randomised, controlled, open-label clinical trial for first-line non-invasive respiratory support modality in critically ill children.

3.2 Setting

Three diverse NHS PICUs in London in England

4. Inclusion and exclusion criteria

The inclusion and exclusion criteria of this study are as described below.

4.1 Inclusion criteria of patients

In order to minimise variation in practice between and within centres predefined, objective criteria were specified to provide clear directions to clinicians to guide the decision on when to start NRS. Eligible patients fell into one of two groups:

Group A (Step-up)

- i. Age >36 weeks corrected gestational age and <16 years, and
- ii. Deemed to require non-invasive respiratory support by the treating clinician for an acute illness, and
- iii. Satisfies one or more of the following criteria:
 - a. Hypoxia (oxygen saturation <92% in $FiO_2 >0.40$, or equivalent). FiO_2 of 0.40 roughly equates to standard unhumidified nasal cannula oxygen delivered at 6 L/min or oxygen delivered via facemask without a rebreather bag at 6-10 L/min
 - b. Acute respiratory acidosis (pH <7.3 with a concomitant $pCO_2 >6.5$ kPa)
 - c. Moderate respiratory distress (use of accessory muscles, subcostal and intercostal recession, tachypnoea for age, grunting)

Group B (Step-down)

- i. Age >36 weeks corrected for gestation and <16 years, and
- ii. Deemed to require non-invasive respiratory support by the treating clinician after extubation, following a spell of invasive ventilation:
 - a. Either immediately after extubation as a 'planned' procedure, irrespective of clinical condition ('planned') or
 - b. Prompted by deterioration in clinical condition within 72 hours after extubation ('rescue'). Clinical parameters to assess the need for NRS in this situation will be similar to point 3 in Group A

4.2 Exclusion criteria of patients

The exclusion criteria are children who:

- i. Are deemed by the treating clinician to require immediate intubation/invasive ventilation due to severe hypoxia, acidosis and/or respiratory distress, upper airway obstruction or recurrent apnoeas
- ii. Have a tracheostomy in place
- iii. Have a pre-existing air-leak syndrome (pneumothorax /pneumomediastinum)
- iv. Have mid-facial/craniofacial anomalies (unrepaired cleft palate, choanal atresia) or had recent craniofacial surgery
- v. Have an agreed limitation of intensive care treatment plan in place ('not for intubation')
- vi. Have been on domiciliary non-invasive ventilation prior to PICU admission
- vii. Have been managed on either HFNC and/or CPAP (or other form of non-invasive ventilation such as BiPAP) in the preceding 24 hours
- viii. Have been previously recruited to this study during the same PICU admission
- ix. Cannot be treated with HFNC
 - a. Unavailability of appropriate sized nasal prongs
 - b. Unavailability of HFNC device
- i. Cannot be treated with CPAP
 - a. Unavailability of right size of face mask, prong or other patient interface
 - b. Unavailability of CPAP device

5. Outcomes

5.1 Primary outcomes

The primary outcomes of this study measure the respective primary objectives stated in section 2.1.

- i. Estimate the number of eligible patients in Group A (step-up) and Group B (step-down)
- ii. Examine the acceptability of using a mixed model of consent (prospective and deferred), i.e. estimate the number of prospective and deferred consent among the treatment groups
- iii. Assess the feasibility of randomising at least 50% of eligible patients, i.e. examine if 50% of the eligible patients were randomised into the trial
- iv. Test the practical aspects of implementing the study protocol in terms of initiation, maintenance and weaning of the study intervention, i.e. estimate:
 - a. Initiation
 - Proportion receiving allocated treatment
 - Time from randomisation to initiation
 - b. Maintenance (excluding patients who did not continue treatment for the full six hours)
 - Proportion at correct pressure/flow rate by Hour 2
 - Proportion with >50% of time at correct pressure/flow rate in first 6 hours
 - c. Weaning
 - Proportion started weaning when should (by next time point)
 - Proportion weaned by prescribed flow rate (HFNC) or pressure (CPAP) according to protocol
- v. Assess whether a modified COMFORT score (COMFORT score minus the respiratory component) can be used to measure patient tolerance to CPAP/HFNC, i.e. estimate:
 - a. Number of completed COMFORT scores
 - b. Number of lower COMFORT scores when not tolerating (within/between patients)

- vi. Assess the feasibility of using the Parental Stressor Scale: PICU (PSS:PPICU) to measure parental stress 24 hours after the initiation of CPAP/HFNC, i.e. estimate:
 - b. Number of questionnaires returned
 - c. Number/quality of questionnaires completed

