7.1 General analysis issues

7.1.1 Analysis population

All analyses will be based on the intention to treat (ITT) principle. The patients will be analysed according to the group they were randomised to, irrespective of whether the treatment allocated was received.

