7.1.2 Analysis software

Analyses will be performed using Stata/SE Version 14.2 for Windows 64-bit x86-64

8. Statistical analysis

Numbers of patients screened, eligible, randomised, consented and withdrawn from the study will be reported by site. Numbers will be reported for Group A and Group B, with Group B split into 'planned' and 'rescue' subgroups. The information will be summarised as a CONSORT flow diagram. Reasons for exclusion and for withdrawal will be summarised, where reported.

Baseline demographic and clinical data will be summarised for the ITT population, for each of the two treatment groups overall and for Group A and Group B. Continuous variables will be summarized as mean (standard deviation) and median (interquartile range) whilst categorical variables will be summarized as number (percent). There will be no statistical testing for any of the summary measures whilst comparing the baseline variables between the treatment groups. The following baseline variables will be compared between the two treatment groups.

- i. Demographics
- ii. Diagnosis
- iii. Prior treatment
- iv. Physiological parameters related to oxygenation
- v. Ventilation, and
- vi. Work of breathing

For full details of included variables see Appendices.

Adherence will be reported as:

- i. Number and percentage of patients receiving the allocated treatment
- ii. Time from randomisation to initiation (separately for groups A and B)
- iii. Number and percentage of patients at correct pressure/flow rate by Hour 2
- iv. Number and percentage of patients with >50% of time at the correct pressure/flow rate in the first 6 hours
- v. Number and percentage of patients who started weaning in whom the fraction of inspired oxygen (FiO_2) was <0.40
- vi. Number and percentage of patients weaned by the correct amount
 - a. HFNC flow rate is reduced by 50%
 - b. CPAP pressure is reduced by 2 cm H_2O

Flow rate (HFNC group) and pressure (CPAP group) over time will be displayed graphically at the timepoints recorded (Hours 0, 1, 2, 3, 4, 5, 6, 12, 24, 36, 48 and 72).

Assessment of the suitability of the modified COMFORT score will be evaluated by:

- i. Number of completed measurements, reported as a percentage of all possible measurements (i.e. all time points when the patient was on HFNC or CPAP in PICU)
- ii. Number and percentage of patients with at least one measurement recorded

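### Both maintenance adherence measures exclude children who stop before six hours; this is not justified for the Hour 2 measure and is missing from Section 8 and Table 3

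*SAP*

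**What the plan says.** Section 5.1 opens by stating that "The primary outcomes of this study measure the respective primary objectives stated in section 2.1". Item iv tests whether the protocol can be put into practice, and part b reads "Maintenance (excluding patients who did not continue treatment for the full six hours". Two measures sit under that restriction: "Proportion at correct pressure/flow rate by Hour 2" and "Proportion with >50% of time at correct pressure/flow rate in first 6 hours".

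Section 8 lists the same two measures under adherence as "Number and percentage of patients at correct pressure/flow rate by Hour 2" and "Number and percentage of patients with >50% of time at the correct pressure/flow rate in the first 6 hours". Neither line carries the restriction. Table 3 gives both as n/N (%) by arm and by Group A, Group B and total, with no footnote on who is left out.

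Section 7.1.1 adds that "All analyses will be based on the intention to treat (ITT) principle".

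The SAP does not say how a child who stops early would be scored. It does not separate stopping for failure or intolerance from stopping because of improvement, and it does not say whether a child who never started counts as excluded.

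**The concern.** Leaving treatment before six hours happens after randomisation. A child may leave because the device was not tolerated or could not be established, and such a child is plausibly less likely to have reached the protocol setting. If so, adherence among those who stayed is better than adherence among all who started. The outcome is meant to inform a full trial about whether the settings can be delivered, and children in whom delivery broke down early are relevant to that question.

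Two further problems need no assumption about why children stop. First, the Hour 2 measure does not require six hours of treatment, so a known value is discarded because of a later event. Second, an analyst working from Section 5.1 and one working from Section 8 and Table 3 could report different percentages for the same primary outcome. The SAP says it is agreed before outcome data are inspected so that data-derived decisions are avoided. An unsettled denominator leaves one such decision open.

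**Working it through.** **1. What the plan supplies.** Section 6 expects 120 children, about 40 in Group A, which leaves 120 − 40 = 80 in Group B. Its event figures reproduce: 40 × 0.20 = 8 intubations and 80 × 0.10 = 8 re-intubations, 16 in all, or 16/120 = 13.3%. The secondary outcome counts these events over 72 hours. The SAP gives no adherence rate, no number stopping before six hours and no reasons for stopping.

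**2. Formula.** Let n be the children starting in an arm, d the number stopping before six hours, a the adherence in those who continue and s the adherence in those who stop.

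- Reported under Section 5.1: a
- Among all starters: [a(n − d) + s·d]/n
- Difference: (a − s) × d/n

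The difference is positive only if s is below a. It is zero when s = a and negative when s exceeds a.

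**3. Range.** Assumed: n = 60 per arm (equal allocation, all start) and a = 80%. Section 5.1 would report 80% in every row. Adherence among all starters would be:

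| Stop early (of 60) | s = 0% | s = 50% | s = 80% | s = 100% |
|---|---|---|---|---|
| 3 | 76.0% | 78.5% | 80.0% | 81.0% |
| 6 | 72.0% | 77.0% | 80.0% | 82.0% |
| 9 | 68.0% | 75.5% | 80.0% | 83.0% |
| 12 | 64.0% | 74.0% | 80.0% | 84.0% |

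Worked cell: 6 stoppers, s = 0: (0.80 × 54 + 0 × 6)/60 = 43.2/60 = 72.0%. The overstatement is (0.80 − 0) × 6/60 = 8 points.

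**4. Unequal stopping.** Suppose 4 children stop in one arm and 12 in the other, and a = 80% in both. With s = 0, equal reported values of 80% correspond to 0.80 × 56/60 = 74.7% and 0.80 × 48/60 = 64.0% among starters. With s = 50% they correspond to 78.0% and 74.0%. The arm with more stoppers need not be the more overstated one:

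- 6 stoppers with s = 0: 0.80 × 6/60 = 8 points
- 12 stoppers with s = 60%: (0.80 − 0.60) × 12/60 = 4 points

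**5. Hour 2.** Section 8 lists flow and pressure as recorded hourly from Hour 0 to Hour 6. A child who stops at Hour 3, 4 or 5 therefore has the readings the Hour 2 measure needs. Only a child already off treatment by Hour 2 poses a scoring question.

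**6. First six hours.** Here the scoring of early stoppers is a real choice. A child at the protocol setting throughout who stops at Hour 4 has 4/6 = 67% of the window and passes. One who stops at Hour 3 has 3/6 = 50%, which is not more than half, and fails. Measured against time on treatment, both score 100%.

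**The case against.** The strongest reply is that the direction of bias is not shown. A reader might infer that adherence is inflated, and inflated most in the arm with more early failures. The SAP does not support either claim. An early stopper may have been at the protocol setting throughout, or may have stopped because of improvement. Steps 3 and 4 of the working show that the bias can be nil or reversed and that the ordering of the arms can flip. Sixteen stops within six hours (4 and 12) would also equal all the intubations expected in 72 hours. Crossovers and recoveries could add stops, but nothing in the SAP supports that timing or split. This part of the reply stands.

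A reader might also infer that a comparison between arms is distorted. Table 3 is descriptive, with no effect estimate, confidence interval or P value. Adherence is not among the outcomes compared by arm in Section 8 or Table 7, and no success threshold is attached to maintenance.

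A third tempting reading is that the restriction breaches intention to treat. Section 7.1.1 explains that principle as follows: "The patients will be analysed according to the group they were randomised to, irrespective of whether the treatment allocated was received". The restriction moves no child between arms, and a denominator of starters is not all randomised children either. The conflict is too weak to carry the point.

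It can also be said that early failures appear elsewhere and that Section 8 merely abbreviates Section 5.1. Treatment failure is indeed reported by arm, but over 72 hours, so it does not show who left before six. Table 3's N would reveal a smaller denominator but not the reason for it. The abbreviation argument is weakened by Section 8 itself, which spells out a restricted denominator for completion of the modified COMFORT score.

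**Conclusion.** The point holds in limited form. The restriction in Section 5.1 is a selection on a post-randomisation event that may overstate adherence. Its direction and size cannot be fixed from the SAP. Under the assumptions in the working, with 3 to 12 of 60 stopping, the effect runs from a 16-point overstatement to a 4-point understatement.

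Two parts rest on no assumption. The restriction is unjustified for the Hour 2 measure, and the denominator of a primary outcome is stated differently in Section 5.1 than in Section 8 and Table 3. Both should be settled before analysis. Neither threatens a formal treatment comparison, because none is planned on these measures.

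**What to change.** - **Hour 2 measure:** remove the restriction. Report it for all children who started allocated treatment, with those already off treatment by Hour 2 shown as their own row.
- **First-six-hours measure:** report all starters, using the share of time on treatment up to six hours that was at the protocol setting. Beside it, keep the six-hour completers as a labelled row. Counting all hours after a failure as off target should not be the only version, because it mixes clinical failure with non-adherence.
- **Early stops:** give the number stopping before six hours by arm, with the reason where recorded.
- **Consistency:** write the same denominators into Section 5.1, Section 8 and Table 3.

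The cost is a few extra rows in Table 3 and revised SAP wording. The measures use settings already scheduled for recording. Reasons for stopping are asked for only where they exist, since the SAP does not show that they are collected. Reported adherence may become less favourable.

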5.2 Secondary outcomes

The secondary outcomes of this study measure the respective secondary objectives stated in section 2.2.

- i. To determine the rate of intubation - i.e. estimate the proportion of children randomised to the intervention or control who need intubation (Group A) or re-intubation (Group B) within 72 hours of randomisation
- ii. To determine the rate of treatment failure - i.e. estimate the proportion of children randomised to the intervention or control who fail the assigned treatment and require either crossover or escalation to other forms of ventilation within 72 hours of randomisation
- iii. To assess safety – i.e. estimate the number of children who experience pre-specified adverse events i.e.
 - a. Pneumothorax
 - b. Pneumomediastinum
 - c. Subcutaneous emphysema
 - d. Abdominal distension
 - e. Nasal or facial trauma
 - f. Facial trauma
 - g. Facial thermal injury
 - h. Respiratory/Cardiac arrest
 - i. Aspirationduring the period they were receiving non-invasive respiratory support
- iv. To assess physiological effects – i.e. estimate changes in:
 - a. oxygenation
 - b. pCO₂ levels

- c. heart rate
 - d. respiratory rate
 - e. and work of breathing
- in the first 24 hours after the initiation of CPAP/HFNC
- v. To assess effects on patient outcome – i.e. estimate:
 - a. length of PICU stay
 - b. hospital stay
 - c. length of invasive ventilation
 - d. length of non-invasive support
 - e. ventilator-free days at day 28
 - f. PICU mortality
 - g. hospital mortality

6. Power calculation

Since this is a feasibility study, no formal sample size calculations was performed. Based on analysis of audit data, we expect around 250 eligible patients over the 6-month period at the three sites. Assuming a 50% recruitment rate, we will have recruited 120 study patients (around 40 patients in Group A). Data from the literature suggests a 20% rate of intubation for Group A (i.e. we expect to see eight intubation events), and a 10% rate of re-intubation for Group B (i.e. we expect to see eight re-intubation events).

7. Statistical methods

7.1 General analysis issues

7.1.1 Analysis population

All analyses will be based on the intention to treat (ITT) principle. The patients will be analysed according to the group they were randomised to, irrespective of whether the treatment allocated was received.

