- iii. Mean (SD) modified COMFORT score at individual time points by tolerating allocated treatment (Yes or No) at that time point
- iv. Mean (SD) across patients of the mean within-patient modified COMFORT score for patients with a highest level of respiratory distress of moderate or severe compared with those with a highest level of none or mild

Assessment of the suitability of the PSS:PICU will be evaluated by:

- i. Number and percentage of parents returning a completed questionnaire
- ii. Number and percentage of returned questionnaires with:
 - a. All questions completed
 - b. >90% of questions completed

The number and percentage of patients experiencing treatment failures, defined as crossover or escalation to other forms of ventilation within 72 hours of randomisation, will be reported for each group. Breakdowns of the numbers of crossovers and escalation (by level of respiratory support) will be reported.

The number and percentage of patients experiencing each pre-specified adverse event (plus any other adverse events as reported) will be summarised for each treatment group. Numbers of severe adverse events and their reported relatedness to treatment will be reported in text.

The physiological effects of treatment will be presented graphically by plotting the mean \pm SD of each physiological parameter at the time points recorded (Hours 0, 1, 2, 3, 4, 5, 6, 12, 24, 36, 48 and 72).

A comparison of outcomes by treatment group will be reported for the following outcome measures:

- i. Intubation within 72 hours
- ii. Treatment failure within 72 hours (separately for crossover and escalation patients)
- iii. Length of PICU stay
- iv. Length of hospital stay
- v. Length of invasive ventilation
- vi. Length of non-invasive support
- vii. Ventilator-free days at day 28
- viii. PICU mortality
- ix. Hospital mortality

Binary outcomes will be reported as the number and percentage in each group, the risk ratio and absolute risk reduction with 95% confidence intervals. Continuous outcomes will be reported as the mean (SD) and median (IQR) in each group and the difference in means with 95% confidence interval.

Differences in treatment effect between Group A and Group B for all outcome measures will be tested as interaction tests (Mantel-Haenszel tests for binary outcomes, interaction terms in linear regression models for continuous outcomes) and presented as forest plots.

9. Reporting conventions

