Group A	XX	XX	XX	XXX
Group B:	XX	XX	XX	XXX
Planned	XX	XX	XX	XXX
Rescued	XX	XX	XX	XXX
Total	XX	XX	XX	XXX
Discontinuation/Withdrawal, n (% of consented)				
Group A	XX	XX	XX	XXX
Group B:	XX	XX	XX	XXX
Planned	XX	XX	XX	XXX
Rescued	XX	XX	XX	XXX
Total	XX	XX	XX	XXX
Number of patients analysed, n (% of randomised)				
Group A	XX	XX	XX	XXX
Group B:	XX	XX	XX	XXX

Planned	XX	XX	XX	XXX
Rescued	XX	XX	XX	XXX

Number of patients analysed but not started treatment, n (% of randomised)

Group A	XX	XX	XX	XXX
Group B:	XX	XX	XX	XXX
Planned	XX	XX	XX	XXX
Rescued	XX	XX	XX	XXX
Total	XX	XX	XX	XXX

n: Number of patients; %: Percentage of patients; N: Total number of patients

Table 1b: Number of patients consented and randomised by treatment group

Variables	HFNC	CPAP	Total
Number of patients randomised, n (% of eligible)			
Group A	XX (XX.X)	XX (XX.X)	XX (XX.X)
Group B:			
Planned	XX (XX.X)	XX (XX.X)	XX (XX.X)
Rescued	XX (XX.X)	XX (XX.X)	XX (XX.X)
Total	XX (XX.X)	XX (XX.X)	XX (XX.X)
Consent obtained, n (% of randomised)			
Group A	XX (XX.X)	XX (XX.X)	XX (XX.X)
Group B:			
Planned	XX (XX.X)	XX (XX.X)	XX (XX.X)
Rescued	XX (XX.X)	XX (XX.X)	XX (XX.X)
Total	XX (XX.X)	XX (XX.X)	XX (XX.X)
Refused consent, n (% of randomised)			
Group A	XX (XX.X)	XX (XX.X)	XX (XX.X)
Group B:			
Planned	XX (XX.X)	XX (XX.X)	XX (XX.X)
Rescued	XX (XX.X)	XX (XX.X)	XX (XX.X)
Total	XX (XX.X)	XX (XX.X)	XX (XX.X)
Death prior to consent, n (% of randomised)			
Group A	XX (XX.X)	XX (XX.X)	XX (XX.X)
Group B:			
Planned	XX (XX.X)	XX (XX.X)	XX (XX.X)
Rescued	XX (XX.X)	XX (XX.X)	XX (XX.X)
Total	XX (XX.X)	XX (XX.X)	XX (XX.X)
Discharged prior to consent, n (% of randomised)			
Group A	XX (XX.X)	XX (XX.X)	XX (XX.X)
Group B:			
Planned	XX (XX.X)	XX (XX.X)	XX (XX.X)
Rescued	XX (XX.X)	XX (XX.X)	XX (XX.X)
Total	XX (XX.X)	XX (XX.X)	XX (XX.X)
Discontinuation/Withdrawal, n (% of consented)			
Group A	XX (XX.X)	XX (XX.X)	XX (XX.X)
Group B:			
Planned	XX (XX.X)	XX (XX.X)	XX (XX.X)
Rescued	XX (XX.X)	XX (XX.X)	XX (XX.X)
Total	XX (XX.X)	XX (XX.X)	XX (XX.X)
Number of patients analysed, n (% of randomised)			
Group A	XX (XX.X)	XX (XX.X)	XX (XX.X)
Group B:			
Planned	XX (XX.X)	XX (XX.X)	XX (XX.X)
Rescued	XX (XX.X)	XX (XX.X)	XX (XX.X)
Total	XX (XX.X)	XX (XX.X)	XX (XX.X)
Number of patients analysed but not started treatment, n (% of randomised)			
Group A	XX (XX.X)	XX (XX.X)	XX (XX.X)
Group B:			
Planned	XX (XX.X)	XX (XX.X)	XX (XX.X)
Rescued	XX (XX.X)	XX (XX.X)	XX (XX.X)
Total	XX (XX.X)	XX (XX.X)	XX (XX.X)

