Work of breathing					
Respiratory distress, n (%)					
	None	XX (XX.X)	XX (XX.X)	XX (XX.X)	XX (XX.X)
	Mild	XX (XX.X)	XX (XX.X)	XX (XX.X)	XX (XX.X)
	Moderate	XX (XX.X)	XX (XX.X)	XX (XX.X)	XX (XX.X)
	Severe	XX (XX.X)	XX (XX.X)	XX (XX.X)	XX (XX.X)

n: Number of patients; %: Percentage of patients; N: Total number of patients;
SD: Standard deviation; IQR: Inter-quartile range

Table 3: Adherence by treatment groups

Variables		HFNC	CPAP
		N = XXX	N = XXX
Initiation:			
Randomised treatment started, n/N (%)			
Group A		XX/XX (XX.X)	XX/XX (XX.X)
Group B		XX/XX (XX.X)	XX/XX (XX.X)
Total		XX/XX (XX.X)	XX/XX (XX.X)
Time from randomisation to initiation (hours)			
Mean (SD)			
Group A		XX.X (XX.X)	XX.X (XX.X)
Group B:			
Planned		XX.X (XX.X)	XX.X (XX.X)
Rescued		XX.X (XX.X)	XX.X (XX.X)
Total		XX.X (XX.X)	XX.X (XX.X)
Median (IQR)			
Group A		XX (XX,XX)	XX (XX,XX)
Group B:			
Planned		XX (XX,XX)	XX (XX,XX)
Rescued		XX (XX,XX)	XX (XX,XX)
Total		XX (XX,XX)	XX (XX,XX)
Maintenance:			
At correct pressure/flow rate by Hour 2, n/N (%)			
Group A		XX/XX (XX.X)	XX/XX (XX.X)
Group B		XX/XX (XX.X)	XX/XX (XX.X)
Total		XX/XX (XX.X)	XX/XX (XX.X)
Treated >50% of time at correct pressure/flow rate in first 6 hours, n/N (%)			
Group A		XX/XX (XX.X)	XX/XX (XX.X)
Group B		XX/XX (XX.X)	XX/XX (XX.X)
Total		XX/XX (XX.X)	XX/XX (XX.X)
Weaning:			
Proportion started weaning in whom FiO ₂ was <0.40, n/N (%)			
Group A		XX/XX (XX.X)	XX/XX (XX.X)
Group B		XX/XX (XX.X)	XX/XX (XX.X)
Total		XX/XX (XX.X)	XX/XX (XX.X)
Proportion weaned by correct amount, n/N (%)			
Group A		XX/XX (XX.X)	XX/XX (XX.X)
Group B		XX/XX (XX.X)	XX/XX (XX.X)
Total		XX/XX (XX.X)	XX/XX (XX.X)

n: Number of patients; %: Percentage of patients; N: Total number of patients;
SD: Standard deviation; IQR: Inter-quartile range

Table 4: Modified COMFORT score and PSS:PICU by treatment group

Variables	HFNC	CPAP
	N = XXX	N = XXX
Modified COMFORT score:		
Modified COMFORT score completed, n/N (% of all eligible time points)		
Group A	XX (XX.X)	XX (XX.X)
Group B	XX (XX.X)	XX (XX.X)
Total	XX (XX.X)	XX (XX.X)
Patients with at least one modified COMFORT score completed, n/N (%)		
Group A	XX (XX.X)	XX (XX.X)
Group B	XX (XX.X)	XX (XX.X)
Total	XX (XX.X)	XX (XX.X)
Modified COMFORT score (Hour 1-6) by tolerating randomised treatment at individual time points, mean (SD) [N]		
Group A		
Yes	XX.X (XX.X) [XX]	XX.X (XX.X) [XX]
No	XX.X (XX.X) [XX]	XX.X (XX.X) [XX]
Group B		
Yes	XX.X (XX.X) [XX]	XX.X (XX.X) [XX]

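### Table 6 divides adverse events counted only on non-invasive support by the full ITT arm, so on-support event percentages are slightly understated

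*SAP*

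**What the plan says.** Section 7.1.1 says "All analyses will be based on the intention to treat (ITT) principle", with children kept in their randomised arm whether or not they received the allocated device. The SAP defines no other analysis set.

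The safety objective (2.2 iii) is "To assess safety of the study treatments during the period the children were receiving non-invasive respiratory support". Outcome 5.2 iii likewise limits the listed events to "the period they were receiving non-invasive respiratory support".

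For reporting, section 8 plans "The number and percentage of patients experiencing each pre-specified adverse event" by treatment group. Table 6 in section 10 shows n (%) for each event under a column-header N for each arm, and its footnote defines N as the total number of patients.

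Tables 1a and 1b carry a row headed "Number of patients analysed but not started treatment, n (% of randomised", so the SAP allows for analysed children who do not start.

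**The concern.** The numerator is tied to exposure and the denominator is not. A child with no non-invasive support at all is an automatic non-event for every pre-specified adverse event, yet still counts in N. Table 6 then understates how often these events occur in children who actually receive support, which is what objective 2.2 iii asks about. If the share with no support differs between arms, the two columns are diluted unequally, and a reader comparing them informally could see a difference that comes partly from non-starting.

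Elsewhere the SAP does match its denominators to exposure. COMFORT completion (section 8) is a percentage of "all time points when the patient was on HFNC or CPAP in PICU", and the maintenance measures (5.1 iv b) are reported "excluding patients who did not continue treatment for the full six hours". Adverse events, whose definition also depends on exposure, get no such treatment.

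**Working it through.** The SAP states no adverse-event rate and no share of children without support, so there is no planned figure to reproduce. The check is direct arithmetic.

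**Inputs**
- Section 6: 120 patients, around 40 of them in Group A, hence about 80 in Group B.
- Assumed: equal allocation, since the SAP gives no ratio. This makes 60 per arm, about 20 in Group A and 40 in Group B.
- Assumed: u, the share of an arm's analysed children who start no support, is 5%, 10% or 15% (3, 6 or 9 of 60).
- Assumed: 6 children with a given event in a whole arm, or 4 in a Group B arm.

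**Formula**

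If r is the risk among children who start support, events = r × N(1 - u). Dividing by N gives

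Table 6 percentage = r × (1 - u).

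The relative understatement is u.

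**Whole arm, 6 events**

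| No support | Table 6 (ITT) | Among starters |
|---|---|---|
| 0 | 6/60 = 10.0% | 6/60 = 10.0% |
| 3 | 6/60 = 10.0% | 6/57 = 10.5% |
| 6 | 6/60 = 10.0% | 6/54 = 11.1% |
| 9 | 6/60 = 10.0% | 6/51 = 11.8% |

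**Group B arm, 4 events, if all the unsupported children are in Group B (an unfavourable case)**

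| No support | Table 6 (ITT) | Among starters |
|---|---|---|
| 3 | 4/40 = 10.0% | 4/37 = 10.8% |
| 6 | 4/40 = 10.0% | 4/34 = 11.8% |
| 9 | 4/40 = 10.0% | 4/31 = 12.9% |

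**Sampling error for comparison.** Exact (Clopper-Pearson) 95% intervals are 3.8% to 20.5% for 6/60 and 2.8% to 23.7% for 4/40. Every shift above lies well inside them.

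**Unequal shares.** If r is the same in both arms but u is 2% on HFNC and 10% on CPAP, the ratio of the Table 6 percentages is (1 - 0.02)/(1 - 0.10) = 0.98/0.90 = 1.09, although the true on-support ratio is 1.

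**Can u be read from the planned tables?** Not exactly. The Table 1a/1b row may include children who started the other device. They are on support and can have a counted event, so the row gives only an upper bound. Table 3 reports "Randomised treatment started, n/N", which concerns the allocated device alone. Neither isolates children with no support at all.

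**The case against.** The strongest reply is that this is a reporting preference. Outcome 5.2 iii asks for a number of children, and no count changes. No risk ratio, interval or test is planned for adverse events, so no inference changes either. The value of u is unknown and may be small: eligibility requires the clinician to judge that support is needed, and children needing immediate intubation, or for whom no suitable device or interface is available, are excluded. ITT denominators also preserve the randomised comparison, and Table 1b lets a reader bound the dilution by arm and group. Finally, dropping non-starters still weights an hour of support the same as several days, so it does not give a rate per unit of exposure. COMFORT completion and maintenance are process measures that need exposure to be defined at all, so they are imperfect precedents.

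Most of this stands, and it limits the point to a minor one. It does not remove it. Section 8 and Table 6 commit to percentages as well as counts, and those percentages can only be pulled downwards by children who were never at risk. An upper bound from Table 1b does not give the on-support figure. The loss of the randomised comparison among starters is a reason to keep the ITT line, not a reason to omit the other.

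**Conclusion.** The concern holds, as a minor point. On the natural reading of section 7.1.1 and Table 6, pre-specified adverse-event percentages equal the on-support percentage times (1 - u). In the assumed whole-arm cases the shortfall is 0.5 to 1.8 percentage points (10.5 - 10.0 to 11.8 - 10.0); in the unfavourable Group B cases it is 0.8 to 2.9 points (10.8 - 10.0 to 12.9 - 10.0). These sizes rest on assumed values of u, assumed event counts and equal allocation. The effect is zero if every analysed child starts some support. Counts are unaffected, and so is the row for other adverse events, for which the SAP states no on-support window.

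**What to change.** Keep ITT for Table 7. In Table 6, for each pre-specified event, add a line of n/N (%) by randomised arm and by Group A/B among children who started any non-invasive support (HFNC, CPAP or other). Identify these children from the data behind length of non-invasive support in Table 7, not from Table 3. Keep the ITT percentage as a second line, and leave the row for other adverse events on ITT.

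The cost is one sentence in section 7.1.1 and one extra line per pre-specified event, with no new data collection. The drawback is that starters are selected after randomisation. If one device is harder to start, its starters may differ from those in the other arm, so the new line describes safety on support and is not a randomised comparison. Showing the ITT line beside it, with a footnote saying so, deals with this.
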